Overview: Using the deidentified fecal, urine and blood samples from Part 1 of above-described parent study, we will perform a MWAS. Healthy humans have unique gut microbial communities; however, we will investigate whether supplementation with GP will promote elements of similarity in the gut microbiota and resulting microbial metabolites (MM), including PAC-derived MM and host-derived MM such as secondary bile acids (BA), that could be linked to healthy states and metabolic resilience. Such data may reveal common ecological or functional rules existing in microbiotas of healthy individuals as well as GP- or host-derived MM biomarkers with diagnostic potential. Below is an example of a MWAS work flow.

Shotgun Metagenomics Workflow

gDNA will be extracted from deidentified fecal samples. Libraries will be constructed followed by high-throughput sequencing on an Illumina HiSeq instrument (Genewiz). Cluster generation, template hybridization, isothermal amplification, linearization, and blocking, denaturing and hybridization of the sequencing primer will be performed according to the workflow specified by service provider. Prinseq (23) will be used to trim and de-duplicate raw reads. Reads that align to the murine/human genome (24) will be removed.

De novo non-redundant metagenomic gene-catalogue construction and gene abundance-profile calculations: High-quality paired-end reads from each sample will be used for de novo assembly with IDBA_UD (25) into contigs of at least 500 bp. Genes will be predicted using MetaGeneMark (26). A non-redundant gene catalogue of microbial genes will be constructed with CD-HIT. Quality reads will mapped onto the gene catalogue using SOAPaligner (27). Aligned results will be sampled and downsized to an appropriate number of reads per sample.

Co-abundance gene groups (CAGs): Individual genes will be binned in to co-abundance gene groups (CAGs) with a canopy-based algorithm (28). Raw CAGs will be removed in the subsequent analyses if they have fewer than 3 genes or 90% of the total canopy profile is distributed in no more than three samples. CAGs with >700 genes will be regarded as bacterial CAGs for further analyses. The principal component analyses of the bacterial CAGs based on the Bray-Curtis distance and Procrustes will be performed with QIIME (29). Abundance of genes identified per sample will be determined to follow changes in gene richness over time course of GP-SPI supplementation.

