4) Statistical analysis: To find the bacteria that respond to GP either positively or negatively (i.e. GP responders) we will omit those strains that are found to change with only SPI supplementation. To further understand how the GP responders affect host metabolic health as a group, we will derive a GP Responder

Index (GRI) based on the abundance and diversity [Heip evenness] of the identified bacteria (36). Data will be subject to two-way repeated measures ANOVA to decipher main effects and interactions between GP and SPI. $P < 0.05$ will be considered significant.

To detect significant differences in metabolites MetaboAnalyst 3.0 software (<http://www.metaboanalyst.ca/>) will be used. Principal components analysis (PCA) will transform original data variables into a smaller number orthogonal variables built from linear combinations to explain most of the data variance and cluster samples from each time-point or group to be analyzed. Significant difference ($p < 0.05$) will be determined within subject at different time-points, within group, and between groups. Variable importance in projection (VIP) scores will be estimated to select metabolites biomarkers from a partial least squares-discriminant analysis (PLS-DA). VIP scores are a weighted sum of PLS weights for each variable and measure the contribution of each predictor variable to the PLS-DA model. Compounds with VIP score > 4 represent metabolites with greatest change, which will be chosen for proof of identity. Before carrying out PCA and PLS-DA analyses, peak intensity will be controlled by a logarithmic transformation, and monitored by Pareto scaling. Methods for data preprocessing and statistical analysis will be optimized and additional corrections and tools will be applied as needed (37; 38).

Co-inertia analysis: To aid interpretation of the relationship between the bacterial responders and metabolomics datasets, they will be integrated using a multivariate method known as co-inertia analysis (CIA) (39). We expect to uncover bacterial species/strain level increases and decreases in GP-SPI-supplemented subjects that correlate with a concomitant increase and decrease in production of their metabolites.

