6.0 Data Management Plan

6.1 Data Analysis

Statistical comparisons will focus on individual and aggregate comparisons with respect to baseline to follow-up change in gut microbiota populations and biochemistry profile in blood and urine samples.

For each outcome, the equality of the outcome means for GP-SPI versus SPI will be tested against a two-directional alternative, controlling the type 1 error at $\alpha = 0.05$. The analyses will be conducted using t-tests for between group analysis and with repeated measures to conduct analysis of variance. Post-hoc tests will be conducted for pairwise comparisons of GP-SPI and SPI employing the Tukey method for controlling the global comparison-wise significance at 0.05 level. Logarithms or other transformations will be applied for data seriously deviating from normality; alternatively, non-parametric analyses may be conducted.

Handling of missing data: The data will be analyzed using the procedures PROC MIXED and PROC GLIMMIX SAS (v 9.3 or later). Thus, mixed effects models for repeated measures will be employed to analyze all available data irrespective of missing or incomplete data attributable to dropouts or other phenomena. In anticipation of the possibility of missing data, we plan to conduct sensitivity analyses that compare our findings against protocol completer analyses and last observation carried forward analyses in addition to investigating characteristics of participants who fail to protocol.

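### If the GP Responder Index is tested in the participants whose data chose its members, its p-value is inflated; and with no stated split by direction, rises and falls can offset

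*Combined protocol and SAP*

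**What the plan says.** The index is described in section 1.3, under the MWAS, in the statistical analysis item (item 4) of the metabolomics workflow.

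- **Selection.** Bacteria are sought that react to GP in either direction: "To find the bacteria that respond to GP either positively or negatively (i.e. GP responders"). Strains that change under SPI alone are left out. No test, threshold or multiplicity rule defines a response.
- **Purpose and content.** The responders are to be treated as one group, with the aim of learning how they bear on the host's metabolic health. The group is summarised in a single measure: "Index (GRI) based on the abundance and diversity [Heip evenness] of the identified bacteria (36"). No sign, weight or division into rising and falling strains is given. The formula is left to the cited source.
- **Test.** The sentence after that reads: "Data will be subject to two-way repeated measures ANOVA to decipher main effects and interactions between GP and SPI". The significance level is 0.05. The sentence does not name the index.
- **Samples.** "Using the deidentified fecal, urine and blood samples from Part 1 of above-described parent study, we will perform a MWAS". No second cohort, held-out subset or cross-validation is mentioned.

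Section 6.1 (Data Analysis) adds that outcomes are "tested against a two-directional alternative, controlling the type 1 error at $\alpha = 0.05". It applies the Tukey method to pairwise comparisons of GP-SPI and SPI, which does not address how strains are chosen for the index.

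**The concern.** There are two separate problems.

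**Selection and testing on the same data.** Strains enter the index because they changed under GP-SPI in these participants. If the index is then tested for change under GP-SPI in the same participants, chance changes that led to selection are counted again as evidence. The nominal 5% error rate no longer applies.

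**No stated direction.** Responders may go up or down, and the co-inertia paragraph in the same section expects both. If they are summed, a real response made of rises and falls can leave the total where it was. Evenness describes how abundance is shared among members. It does not say whether they responded.

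The index is the plan's group-level summary of the responders. A significant change could therefore reflect selection alone, and a flat index could hide a real response.

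**Working it through.** **Plan's own figure.** There is none for the index. The sample-size statement in section 1.5 (16 subjects, power 96.2%) concerns *A. muciniphila* relative abundance only and has no bearing here.

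**Inputs from the documents.** 30 enrolled (section 1.3) and 20% loss (section 4.3) give 30 × (1 − 0.20) = 24 completers. Alpha is 0.05, two-sided. Stool is sampled on days −5, 0, 2, 4, 6, 8 and 10.

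**Assumed inputs.** 50 to 300 candidate strains; selection at uncorrected p < 0.05; log-normal abundances closed to proportions, with between-subject SD 1, within-subject SD 0.7 or 1.0 and between-strain SD 0.5 to 2.0, all on the log scale.

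**Step 1: no true effect, selection and test in the same participants.** A strain is a responder if a paired t-test of log abundance, day 10 against day 0, gives p < 0.05. It is dropped if day 0 against day −5 also gives p < 0.05, which mimics the SPI omission. The index of the remaining strains is tested by paired t on the same 24 people. There were 600 runs per setting, and rates are among runs with at least two strains selected.

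| Strains | Within SD, between-strain SD | Log pooled abundance | Heip alone | Abundance × Heip |
|---|---|---|---|---|
| 100 | 0.7, 1.5 | 58.6% | 21.4% | 59.7% |
| 100 | 1.0, 2.0 | 64.1% | 17.8% | 63.0% |
| 100 | 1.0, 0.5 | 39.7% | 7.6% | 48.7% |
| 300 | 0.7, 1.5 | 46.0% | 18.0% | 54.2% |
| 300 | 1.0, 2.0 | 55.3% | 22.0% | 59.7% |
| 300 | 1.0, 0.5 | 31.0% | 5.8% | 44.0% |

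If runs with fewer than two selected strains are counted as not significant, pooled abundance is still significant in 31 to 56%. With 50 strains and no SPI-omission step the pooled rate was 73 to 75%. The product column is one possible way of combining the two parts; the plan does not say how they are combined.

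**Step 2: no true effect, selection in one half and test in the other.** With 100 or 300 strains, pooled abundance was significant in 4.8 to 5.1% and Heip in 5.0 to 5.4%. The nominal level is restored.

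**Step 3: a stricter selection rule.** With selection at a 5% false discovery rate, two or more false responders appeared in 5 of 2000 null datasets (0.25%). The inflation in step 1 therefore depends on a lenient rule. The plan states neither kind.

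**Step 4: direction.** Heip evenness = (exp(H) − 1)/(S − 1), where H = −Σ p ln p and S is the number of strains. Let one strain go from 0.1% to 0.4% (the planning values in section 1.5) and another from 0.4% to 0.1%.

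- Pooled abundance: 0.1 + 0.4 = 0.5% before, and 0.4 + 0.1 = 0.5% after.
- Evenness: p = 0.2 and 0.8 both times, so H = 0.500, exp(H) = 1.649 and Heip = 0.649/1 = 0.649 before and after.

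Both strains changed four-fold and neither component moved.

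**Step 5: evenness when one member rises four-fold.**

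- Ten equal strains: Heip goes from (10 − 1)/9 = 1.00 to (8.486 − 1)/9 = 0.83. Abundance rises by 13/10 − 1 = 30%.
- One strain going from 0.1% to 0.4% beside nine at 0.5%: Heip goes from 0.948 to 0.998.

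The same rise can lower or raise evenness, depending on where the strain starts relative to the others.

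**Step 6: cost when the effect is real.** With 10 strains up and 10 down out of 100 (log change 1.0) and selection in the other half, pooled abundance detected the effect in 21% of trials and Heip in 19%. Risers alone detected it in 67%, and a direction-signed index in 99.8%.

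**The case against.** **The test is inferred.** The ANOVA sentence speaks of data in general, and the stated purpose of the index is to understand host metabolic health. This stands as a limit. The sentence directly follows the definition of the index and no other test of it is given, so the reading is natural but not explicit. Relating the index to a host measure that played no part in selection is not inflated by this selection alone.

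**The formula is unseen.** The cited source may separate or sign the strains. That also stands, and it is why the direction point is limited to the index as the protocol describes it.

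**Stronger readings that the documents do not support.**

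- A reader might infer that selection guarantees a significant result. For the pooled index described, it does not: chance rises and falls partly cancel. Rates of 98 to 99.7% arise for an index of selected risers only, and 100% for a signed index. The plan describes neither.
- A reader might infer that evenness must fall if *Akkermansia* blooms. At the planned four-fold rise it can go either way (step 5). Even where it falls to 0.83, abundance times evenness still rises by 8% (1.30 × 0.83 = 1.08).
- A reader might infer that nothing about the responders can be interpreted. The co-inertia analysis in the same section looks at strain-level increases and decreases, so direction is kept there.

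**Consequence is limited.** This is an exploratory step in a pilot, and the listed MWAS endpoint is to collect and store samples. That lowers the priority but does not remove the problem.

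**Conclusion.** The concern holds in a bounded form. If the ANOVA is applied to the index, a test of GP or time on it is not a 5% test. With 24 completers, 50 to 300 strains and uncorrected selection at p < 0.05, the false-positive rate is about 30 to 75% for pooled abundance and about 6 to 22% for Heip evenness alone, against about 5% when selection and testing use different participants. FDR-controlled selection would seldom yield any responder under a global null, but none is stated. Separately, an index with no sign or split can stay flat when strains truly respond in opposite directions, and evenness is not a measure of response.

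The exact rates rest on assumed strain counts, spreads and selection rule, and on a two-day paired test in place of the full ANOVA. Confidence is moderate because the tested variable and the formula are inferred. The primary 16S endpoint is not affected.

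**What to change.** Amend the paragraph in section 1.3 as follows.

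1. State the rule that makes a strain a responder, including its error control, and write out the index formula.
2. Define one index for rising strains and one for falling strains, or their log-ratio, so that a higher value has one meaning. Report evenness separately.
3. For any p-value on change in an index, choose its members without the participant being scored: either cross-fitting, with a permutation test that repeats the selection, or a split by participant. Otherwise report the change descriptively with no test.
4. Name the variable to which the ANOVA applies.

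Items 2 and 3 belong together: a risers-only or signed index tested in the selecting sample would be significant almost every time by construction.

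The cost is one paragraph of wording and some computing, with no new samples or visits. The downside is that a cross-fitted index will look weaker than the in-sample one. A simple split of 24 completers would leave 12 for selection and 12 for testing, which is a reason to prefer cross-fitting.

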1.6 Study Variables

A. Independent Variables, Interventions, or Predictor Variables

The independent variables will be supplementation with SPI or GP-SPI.

B. Dependent Variables or Outcome Measures

Outcome measures are gut microbial community analyses, CMP results, urine and serum metabolites, and bacterial genes, species/strains.

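### No error control is committed to across metabolites, taxa and genes, and the 16S primary endpoint is not tied to one test

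*Combined protocol and SAP*

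**What the plan says.** **Metabolites (section 1.3, MWAS, Statistical analysis).** The threshold is direct: "Significant difference ($p < 0.05$) will be determined within subject at different time-points, within group, and between groups". A separate rule concerns identification: "Compounds with VIP score > 4 represent metabolites with greatest change, which will be chosen for proof of identity". The paragraph closes by saying that "additional corrections and tools will be applied as needed (37; 38").

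**Bacteria (same section).** Strains that change on SPI alone are dropped. The next sentence begins "To further understand how the GP responders affect host metabolic health as a group, we will derive a GP Responder" Index (GRI). Unspecified data then go to a two-way repeated-measures ANOVA, where "P < 0.05$ will be considered significant". No cut-off is given for calling a strain a responder.

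**General rule (section 6.1).** "For each outcome, the equality of the outcome means for GP-SPI versus SPI will be tested against a two-directional alternative", with type 1 error held at 0.05. Post-hoc pairwise comparisons of GP-SPI and SPI are made "employing the Tukey method for controlling the global comparison-wise significance at 0.05 level". Mixed models are to use all available data.

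**What an outcome is (section 1.6).** "Outcome measures are gut microbial community analyses, CMP results, urine and serum metabolites, and bacterial genes, species/strains".

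**Primary endpoint (section 1.3, Endpoints).** Gut microbiota composition by 16S sequencing, with no metric, taxon, day or test. Section 1.5 bases the sample size on *A. muciniphila* with a Hotelling-Lawley test. It then plans a search through phyla, genera and specific microbes. The hypothesis in section 1.1 adds other genera without listing them.

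**The concern.** A per-feature threshold of 0.05 produces false positives in proportion to the number of features examined. Here that number is large by design: the metabolomics is untargeted, uses two column types and both ionisation modes, and aims at the widest possible coverage. None of the safeguards in the text sets an error rate across features.

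The primary endpoint raises the same problem in another form. No taxon, day or test is fixed, so any phylum or genus below 0.05 could be reported as the effect of GP-SPI on composition. At stake are the credibility of the published list of responding taxa and metabolites, and the laboratory work spent following up chance findings. A pre-stated *Akkermansia* test would not be affected, but the plan never designates one as primary.

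**Working it through.** **1. The plan's own figure.** Section 1.5 gives a mean rising from 0.1% to 0.4%, SD 0.5%, two-sided alpha 0.05, n = 16 and power 96.2%. The within-subject correlation ρ is not stated. For one paired contrast, the SD of change is 0.5 × √(2(1 − ρ)) and the noncentrality is 0.3 × √n / SD of change. Power from the noncentral t:

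| ρ | n = 16 | n = 24 |
|---|---|---|
| 0 | 36% | 51% |
| 0.5 | 61% | 80% |
| 0.8 | 94% | 99% |

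The stated 96.2% is returned at ρ of about 0.82. Hotelling-Lawley tests over three, six or seven time points with equal correlations need about 0.86 to 0.88. The figure is therefore attainable but cannot be confirmed. It covers one taxon and one test. The 24 completers are 30 enrolled less 20% (section 4.3).

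**2. Metabolites.** Expected false positives per contrast are 0.05 × the number of null features: 0.05 × 1,000 = 50. Correlation between features does not change this expectation. The documents give no feature count, so this is a rate and not a forecast.

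**3. 16S genera.** The chance of at least one false positive among m independent null tests is 1 − 0.95^m. The value m = 9 is *Akkermansia* plus the eight genera named in section 1.4; 20 and 45 are assumptions. The last column is simulated with one common factor, n = 24 and one test per genus.

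| m | Independent | Genera share 30–50% of variance |
|---|---|---|
| 9 | 37% | about 29–33% |
| 20 | 64% | about 44–55% |
| 45 | 90% | about 61–79% |

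**4. What false discovery rate control would do.** Assumed: 45 independent genera, 5 true responders, 24 completers, one contrast per genus, Benjamini-Hochberg at 5%. A standardised change of 0.6 is the plan's 0.3/0.5 when ρ = 0.5. Simulated averages:

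| Standardised change | Rule | True found (of 5) | False found | Chance of any false genus |
|---|---|---|---|---|
| 0.6 | P < 0.05 | 4.0 | 2.0 | 1 − 0.95^40 = 87% |
| 0.6 | FDR 5% | 1.9 | 0.15 | about 13% |
| 0.8 | P < 0.05 | 4.8 | 2.0 | 87% |
| 0.8 | FDR 5% | 3.8 | 0.2 | about 20% |

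**5. Effect of widening the family.** If all five GP-SPI days against day 0 enter the family at change 0.6, the true genera found on day 10 fall from 1.9 to about 0.8 (effect on day 10 only) or 1.0 (linear rise).

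**The case against.** The case for leaving the plan alone has real content. This is a pilot meant to inform a later controlled study, and the MWAS workflow is introduced as an example. The only MWAS-related endpoint is to collect and store samples. Candidate associations go on to in vitro testing, and metabolites must also pass the VIP and identification steps. One reference cited for further corrections is, by its title, a guideline on univariate analysis of untargeted LC/MS data. All of this limits the harm. It does not supply an error rate: applying corrections as needed is not a commitment, and the documents do not show what the reference would require. Proof of identity shows what a compound is, not that GP-SPI changed it.

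Four stronger readings are tempting, and the documents do not support them:

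- **That the MWAS section itself tests every strain and gene at 0.05.** The ANOVA sentence follows directly on the GRI and may refer to it. For strains and genes the point rests on reading sections 6.1 and 1.6 together. Only the metabolite threshold is direct.
- **That false metabolites pass through p < 0.05 into the co-inertia analysis.** That analysis joins the bacterial responders to the metabolomics data, and nothing makes the threshold the entry rule.
- **That the GRI is tested on the samples that selected its members.** The plan does not say that the GRI is tested for a GP effect.
- **That Benjamini-Hochberg would cut the chance of any false genus to about 5%.** That holds only if every genus is null. With true responders present it is about 13% to 20% in the example above.

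**Conclusion.** The point holds and should be fixed before the data are analysed. The plan sets 0.05 per metabolite and, through sections 6.1 and 1.6 together, per bacterial feature. It commits to no control across features and fixes no primary 16S test. The rate of 50 false positives per 1,000 null features per contrast needs no assumption about correlation. The 37%, 64% and 90% assume independent null genera, and the counts of 20 and 45 are illustrative. The consequence is moderate: chance findings in an exploratory list and an open choice of primary result, in a pilot whose leads are to be tested again.

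**What to change.** **1. Features.** In the MWAS statistical paragraph and section 6.1, replace the per-feature 0.05 with Benjamini-Hochberg control at 5% within each of five families: 16S taxa; strains and co-abundance gene groups; genes and pathways; serum metabolites; urine metabolites. Use one pre-named test per feature, such as day 10 versus day 0 (day 11 versus day 0 for serum) or one overall time test. Treat other days as descriptive. Report the estimate, confidence interval, raw P and adjusted P for every feature. VIP then only ranks compounds for identification. CMP safety results stay outside these families.

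**2. Primary test.** Name one test at two-sided 0.05: the change in *Akkermansia* relative abundance from day 0 to day 10, as a contrast from the section 6.1 mixed model. A standard Hotelling-Lawley test needs complete series, which sits badly with section 6.1's use of all available data and the expected 20% loss. State whether the target is *A. muciniphila* (section 1.5) or *Akkermansia* spp. (section 1.1). Restate the power with its assumed correlation. Label other taxa exploratory.

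**3. GRI.** State whether it is tested for a GP effect.

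**Cost.** Wording only, with no new samples or subjects. The scientific price is lost sensitivity: in the example, 1.9 instead of 4.0 true genera at change 0.6, and 3.8 instead of 4.8 at 0.8. The loss is larger if several days enter one family, which is why one test per feature matters. Raw P values keep weaker leads visible. Control is within families: with all five wholly null and independent, the chance of any false call is 1 − 0.95^5 = 23%.

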b) Urine samples (100 µL aliquots) will be centrifuged (10,000 g for 10 min at 4 °C) to remove particulates followed by dilution with water (1:1 to 1:3 vol/vol). Samples (10 µl) will be added to 10 ml of ACN and centrifuged at 3000 g for 15 min. The supernatant will be collected, dried, reconstituted in 500 µl of ethanol (50 % v/v) containing 0.1 % ascorbic acid and (w/v) and transferred to HPLC vials for untargeted analyte detection by high resolution MS (20; 35).

To deplete common matrix interferences such as phospholipids, salts, and proteins and optimize sample preparation each sample supernatant produced in a) and b) may also be loaded to Oasis Prime HLB Cartridges (Waters). Sample preparation methods will be tested.

2) Chromatographic separation and high-resolution mass spectrometry (MS): Triplicates (i.e. technical replicates) of each serum or urine sample will be separated on a Dionex UltiMate 3000 Binary Rapid Separation UHPLC with Diode Array Detector with a reverse phase (RP) C18 column for retention of medium polar and non-polar analytes as well as a hydrophilic interaction chromatography (HILIC) column for retention of highly polar metabolites (35). Separation of samples on RP and HILIC columns prior to MS will provide more comprehensive metabolome coverage. To detect the greatest number of metabolites, gradient elution protocols will be optimized separately for serum and urine samples. Chromatographic separations will be followed by MS using a Thermo Scientific Q Exactive Plus Orbitrap high resolution mass spectrometer. The orbitrap provides high mass accuracy (1–2 p.p.m.), resolution up to 100,000 and dynamic range of 5,000. Data will be collected in both positive and negative ESI modes (mass range of 100–2,000 m/z).

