4.3 Number of Subjects

A. Total Number of Subjects

30 subjects will be enrolled after successfully passing screening. The anticipated lost to follow-up rate for this study will be 20% (i.e. 6 non-completers)

B. Total Number of Subjects If Multicenter Study

N/A

C. Feasibility

We expect to recruit the majority of our participants from the New Brunswick campus of Rutgers University. With a relatively flexible study schedule and no particularly stringent eligibility criteria, we do not anticipate difficulties in engaging interest and accommodating schedules of participants. We conservatively expect a recruitment rate of 3-6 participants per month over 6 months.

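### The fixed VIP > 4 rule for choosing metabolites is a relative cut, not a measure of change: it can miss most of a broad response and can select features by chance

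*Combined protocol and SAP*

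**What the plan says.** The rule is in section 1.3, Metabolomics Workflow, item 4 (Statistical analysis). The stated purpose of the score is selection: "Variable importance in projection (VIP) scores will be estimated to select metabolites biomarkers from a partial least squares-discriminant analysis (PLS-DA". The score is then described: "VIP scores are a weighted sum of PLS weights for each variable and measure the contribution of each predictor variable to the PLS-DA model". The cut follows: "Compounds with VIP score > 4 represent metabolites with greatest change, which will be chosen for proof of identity". For preprocessing, "peak intensity will be controlled by a logarithmic transformation, and monitored by Pareto scaling".

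The paragraph does not say where 4 comes from, how many PLS components will be used, or whether the model will be cross-validated or tested by permutation. Significance at p < 0.05 is listed separately and "will be determined within subject at different time-points, within group, and between groups"; it is not a condition for passing the VIP rule, and no multiplicity method is named there. The paragraph ends on an open allowance: "Methods for data preprocessing and statistical analysis will be optimized and additional corrections and tools will be applied as needed".

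**The concern.** The plan reads VIP > 4 as marking the metabolites that changed most. By the plan's own description, VIP measures a variable's contribution to the model, which is relative to every other variable in it. Whether a metabolite passes therefore depends on how many others moved, and the score gives neither the size nor the significance of its own change.

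A broad response is plausible here. The assay is untargeted, uses two column types, and "Data will be collected in both positive and negative ESI modes". The plan also expects many metabolites to appear as conjugates, so one parent compound can produce several features. The rule becomes less sensitive as the response widens. In the other direction, a PLS-DA with far more features than samples can separate two time points in pure noise, and nothing in the plan would reveal that. At stake is the list of candidate biomarkers taken on to identity confirmation.

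**Working it through.** The plan gives no derivation of 4, so there is no figure to reproduce.

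**Inputs from the documents.** The cut is VIP > 4 after log transformation and Pareto scaling (section 1.3). On numbers, "30 subjects will be enrolled after successfully passing screening" (section 4.3), with 20% expected loss: 30 × 0.8 = 24 completers. Serum is compared between days 0 and 11 (section 1.8), giving 24 × 2 = 48 samples.

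**Assumed inputs.** The documents do not give the number of features p (500 to 5,000 tried), the spread of feature variances, within-person correlation or effect sizes.

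**Step 1: algebra, no assumptions.** For p features and components a with explained sum of squares SS_a and unit-length weights w:

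VIP_j² = p × Σ_a(SS_a × w_ja²) / Σ_a SS_a, with Σ_j w_ja² = 1.

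Summing over features gives Σ_j VIP_j² = p, so the mean of VIP² is 1. VIP > 4 means VIP² > 16. If k features pass, 16k < p, so k < p/16, or 6.25%. That is at most 31 of 500, 124 of 2,000 or 312 of 5,000.

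If a share f of features responds equally and the rest carry no weight, VIP = 1/√f:

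| Share changed | 2% | 5% | 6.25% | 8% | 10% | 20% |
|---|---|---|---|---|---|---|
| VIP | 7.07 | 4.47 | 4.00 | 3.54 | 3.16 | 2.24 |

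The size of the change does not appear. A larger common response does not raise the score.

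**Step 2: equal true effects, simulated.** 24 participants, two time points, 2,000 features, feature log-SD 0.3 to 1.5, within-person correlation 0.5, log and Pareto scaling, two components, a 4-fold rise in every changed feature. Ranges cover separate sets of 40 and 60 runs.

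| Share changed | Changed features passing VIP > 4 |
|---|---|
| 2% | 85 to 93% |
| 5% | 36 to 50% |
| 8% | 0.1 to 0.3% |
| 10% and 20% | 0% |

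Paired tests with false-discovery control found 96 to 99.8% of the changed features in the same data.

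**Step 3: unequal true effects, simulated.** With 2,000 features and half-normal effects of scale 1 or 2 SD, 20% changed (400 features) gave about 12 to 21 selected: 12/400 = 3%, 21/400 = 5%. With 30% changed (600 features), about 1 to 12 were selected, and the list was empty in 0 to 16% of runs. In the Step 2 set-up with unequal fold changes, the list was never empty at 2% to 20% changed and held about 12 to 36 features, all truly changed.

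**Step 4: nothing changed, simulated.** Mean number of features selected, over 1, 2 or 5 components, with and without correlated blocks (60 runs per setting). Spread is the SD of the log feature SDs.

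| Spread | p = 500 | p = 2,000 | p = 5,000 |
|---|---|---|---|
| 0 | 0 | 0.02 to 0.07 | 0.05 to 0.35 |
| 0.3 | 0.02 to 0.10 | 0.25 to 0.53 | 0.88 to 1.23 |
| 0.5 | 0.02 to 0.47 | 0.95 to 1.8 | 3.6 to 5.0 |
| 0.8 | 0.5 to 1.4 | 3.8 to 6.0 | 12.3 to 14.4 |

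Variance spread matters because Pareto scaling divides by the square root of the SD: a chance shift proportional to the SD keeps a weight proportional to √SD, so high-spread features are favoured under noise. The worst cells are still only about 0.3% of features (14.4/5,000 = 0.29%; 6.0/2,000 = 0.30%).

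In the Step 2 set-up with no effect, the mean was 0.5 to 0.8 features, and 53 to 65% of runs selected nothing.

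**Step 5: model fit in noise.** In the same no-effect set-up, R2Y was 0.99 while leave-one-participant-out accuracy was 48%, which is chance.

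**The case against.** The strongest reply is that a short list of strong responders is what a screen for identity confirmation needs, and that VIP > 4 usually gives one. This largely stands for unequal effects: in Step 3 the list was rarely or never empty, and in the Step 2 set-up it held no false features. Failing to list all 400 changed features is not in itself a failure of such a screen.

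Second, VIP is not the only route to a metabolite. Section 1.3 also plans significance tests within subject over time and looks for metabolites significantly raised in blood after intake, section 1.8 plans targeted as well as untargeted metabolomics, and section 6.1 specifies mixed models. This stands, and it limits the consequence. It does not repair the rule: the p < 0.05 tests are not joined to the VIP selection, and the allowance for additional corrections names no method and does not withdraw the fixed cut.

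Third, this is a pilot, and the related secondary endpoint is only to collect and store samples for the association study. That also stands. The rule does not touch the 16S primary endpoint, the safety panel or the sample size.

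**Conclusion.** The point holds in limited form. That VIP > 4 is a relative cut which fewer than 6.25% of features can pass is algebra and needs no assumption. Reading it as greatest change is therefore wrong, and the plan neither calibrates nor validates the model behind it.

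Two stronger readings are tempting, and the documents do not support either. A reader might infer that a broad response would always leave the list empty. That needs roughly equal effects and similar variances across responders, which the documents do not state; with unequal effects some strong responders usually survive, although most changed features are missed. A reader might also infer that a null study will always produce candidates. It can, but this depends on feature count and variance spread, and the documents give neither. With the Step 2 variances and correlation and no effect, 90 to 97% of runs at 500 features selected nothing; at 5,000 features with spread 0.5, 97 to 100% of runs selected at least one.

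The simulated sizes rest on the assumed inputs above. The consequence is confined to which compounds this exploratory analysis sends for identity confirmation. The rule should be replaced, but the trial's main conclusions do not depend on it.

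**What to change.** Delete the VIP > 4 cut. Select metabolites by a paired within-participant test on log intensity with false-discovery-rate control. For serum, compare day 11 with day 0. For urine, use a repeated-measures model over days 0 to 10, or day 10 against day 0. Order the metabolites that pass by the paired statistic or by fold change, and send them for identification up to laboratory capacity.

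Do not simply rank on raw log change and take the top compounds. A top-20 list always contains 20 candidates even when nothing has changed, and it favours features with a large spread.

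Keep PLS-DA and VIP for ranking or display only. State the number of components, cross-validate with whole participants left out, and report a permutation p-value that respects the pairing.

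The cost is one paragraph of analysis text and a little more analysis work, with no new samples. The PLS-DA plot will look less clean once validated.
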